### 6.2.4 Treatment of study treatment overdose

Overdose is defined as the dose administered at the dose higher than the maximum daily dose (150 mg) of eltrombopag specified in the study protocol.

When overdose is suspected, perform symptomatic therapy and supportive therapy as needed. At overdose, moreover, administer the antacids containing metallic cation such as calcium, aluminum or magnesium to inhibit absorption of eltrombopag. Hemodialysis is not expected to enhance the elimination of eltrombopag because eltrombopag is not significantly renally excreted and is highly bound to plasma proteins. There is no antidote specific to eltrombopag.

## 6.3 Subject numbering, treatment assignment, randomization

### 6.3.1 Subject numbering

Each subject is identified in the study by a Subject Number (Subject No.), that is assigned when the subject is first enrolled for screening and is retained as the primary identifier for the subject throughout his/her entire participation in the trial. The Subject No. consists of the Center Number (Center No.) (as assigned by Novartis to the investigative site) with a sequential subject number suffixed to it, so that each subject is numbered uniquely across the

entire database. Upon signing the informed consent form, the subject is assigned to the next sequential Subject No. available.

### **6.3.2 Treatment assignment, randomization**

This is a single arm, non-randomized study.

Upon completion of all the required screening assessments, eligible subjects will start eltrombopag treatment at Day 1.

### **6.4 Treatment blinding**

This is a single arm, open label study.

### **6.5 Dose escalation and dose modification**

#### **6.5.1 Dose modifications**

Eltrombopag treatment will be started at a dose of 25 mg/day, and the dose will be titrated in the order of 50 mg, 75 mg, 100 mg, 125 mg and 150 mg/day according to the platelet count of each subject. The criteria for dose adjustment and schematic are shown in [Table 6-3](#) and [Table 6-4](#).

It is allowed to discontinue or reduce eltrombopag based on the discretion of the investigator (sub-investigator) regardless of these criteria when they judge that it is needed due to adverse event.

**Table 6-3 Criteria for dose adjustment of eltrombopag between Week 1 and Week 26**

Standards of platelet count	Dose adjustment
At 2 weeks or more of administration, the platelet count is $< 50 \times 10^9/L$ , or the amount required for platelet transfusion does not decrease.	Titrate the dose by 25 mg each every 2 weeks up to 150 mg/day.
At 2 weeks or more of administration, the platelet count is $\geq 50 \times 10^9/L$ , and is $\leq 100 \times 10^9/L$ .	Maintain the dose.
The platelet count is $> 100 \times 10^9/L$ under no blood transfusion	Reduce the dose by 25 mg each every 2 weeks until the platelet count can be maintained at $100 \times 10^9/L$ or lower.
The platelet count is $> 200 \times 10^9/L$ under no blood transfusion	Interrupt the drug until the platelet count becomes $< 50 \times 10^9/L$ . Thereafter, restart administration at the dose 25 mg lower (The restarting dose is 25 mg/day if the dose at interruption was 25 mg/day).

If dose has increased to 150 mg/day at Week 12, the subject would maintain the maximum dose as 150 mg/day from Week 13 to Week 26. When dose decrease under 25 mg/day is needed, eltrombopag treatment should be interrupted until the platelet count becomes less than  $50 \times 10^9/L$ .

The criteria for dose adjustment of this drug after Week 26 are shown in [Table 6-4](#).

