## 4.2 Rationale for dose/regimen and duration of treatment

### 4.2.1 Rationale for dose/regimen

Eltrombopag 25 mg once daily has been selected as the starting dose for this study because this regimen has been safe and effective in increasing platelet counts in East Asian patients with HCV and chronic ITP. The dose can be increased by 25 mg/day every 2 weeks according to the platelet count to a maximum dose of 150 mg/day in Chinese SAA patients based on the following considerations:

- In the ETB115AUS28T study, an IIT conducted by the National Heart, Lung, and Blood Institute/National Institutes of Health (NHLBI/NIH), the initial dose is 50 mg daily, to a maximum dose of 150 mg daily. Eltrombopag was tolerated well; the majority of subjects (40/43) required escalation to the maximum dose of 150 mg. The most common AEs observed in this study largely reflect the well-known safety profile of eltrombopag and events expected in this patient population. A total of 17 subjects (40%) were determined by the investigator as having met the hematologic response criteria in at least 1 lineage at the primary response assessment.

- A clear dose and exposure response was seen for eltrombopag of 10-200 mg for healthy subjects and 30-75 mg for ITP and HCV patients respectively. In the above dose range, eltrombopag was tolerated well.
- In the ETB115AUS28T study, the eltrombopag could be increased to 150 mg/day to achieve the desired platelet count target. Meanwhile, to ensure subject safety, it is allowed to discontinue or reduce eltrombopag based on the subjects' tolerance. The current study uses a dose escalation scheme in which subjects are exposed to the lowest dose necessary to achieve the desired platelet count target.

Modified dosing for subjects of East Asian heritage (i.e. Japanese, Chinese, Taiwanese and Korean) has been implemented for the following reasons:

- In healthy Japanese subjects, plasma eltrombopag AUCtau was approximately 80% higher when compared to non-Japanese healthy subjects who were predominantly Caucasian.
- Similarly, in patients with ITP, plasma eltrombopag exposure was approximately 70% higher in East Asian (i.e. Japanese, Chinese, Taiwanese and Korean) subjects as compared to non-East Asian subjects who were predominantly Caucasian.
- In Japanese patients with AA, plasma eltrombopag exposure is similar to the reported values in Japanese ITP patients (ETB115E1201).

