These dosing recommendations limit exposure by utilizing the lowest effective dose, discontinuing treatment for non-responding patients and tapering treatment in patients with trilineage response.

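### The 150 mg/day sentence under Protocol Table 6-3 carries no platelet exception and, taken literally, conflicts with the table's own reduction and interruption rules in Weeks 13 to 26

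*Protocol*

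**What the plan says.** Protocol Section 6.5.1 starts eltrombopag at 25 mg/day, titrates it through 50, 75, 100 and 125 to 150 mg/day by platelet count, and refers to Tables 6-3 and 6-4 for the criteria. Table 6-3 covers Weeks 1 to 26 and has four rows:

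- Count below 50 × 10⁹/L, or no fall in the platelet transfusion requirement: "Titrate the dose by 25 mg each every 2 weeks up to 150 mg/day".
- Count from 50 to 100 × 10⁹/L: keep the dose.
- Count above 100 × 10⁹/L without transfusion: "Reduce the dose by 25 mg each every 2 weeks until the platelet count can be maintained at" 100 × 10⁹/L or lower.
- Count above 200 × 10⁹/L without transfusion: "Interrupt the drug until the platelet count becomes" lower than 50 × 10⁹/L, then restart 25 mg lower.

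Below the table, for a subject whose dose has increased to 150 mg/day at Week 12, the protocol adds that "the subject would maintain the maximum dose as 150 mg/day from Week 13 to Week 26". The next sentence turns to the bottom of the dose range: "When dose decrease under 25 mg/day is needed, eltrombopag treatment should be interrupted".

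**The concern.** The sentence has its own trigger (150 mg/day at Week 12) and its own time window (Weeks 13 to 26), and that window lies wholly inside the period the table covers. It does not say that it is subject to the table, and it mentions no platelet count. A site that gives it literal effect would hold 150 mg/day at a count where the table requires a lower dose or none.

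The conflict sits at the highest permitted dose and concerns the rules that bring that dose down. The protocol gives its own reasons for wanting those rules clear. Section 1.3 reports eltrombopag exposure about 50% to 90% higher in Asian than in non-Asian patients. Section 1.2 describes the safety profile in the Japanese study for doses up to 100 mg/day. Section 9.1.1 makes thromboembolism a mandatory reason to stop treatment.

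**Working it through.** There is no plan figure to reproduce. The check asks whether the sentence can apply at all, and then compares the two instructions by platelet count.

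**Can the condition be met?** The inputs from Section 6.5.1 and Table 6-3 are a start at 25 mg/day, steps of 25 mg, at least 2 weeks per step, and a top dose of 150 mg/day.

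- Steps needed: (150 − 25) / 25 = 5.
- Time needed without a hold: 5 × 2 = 10 weeks, so the first 150 mg dose falls on Day 1 + 5 × 14 = Day 71.
- Day 71 is before Week 12 on either of the protocol's week numberings. Table 8-1 places Week 13 at Day 92, so Week 12 is Day 85. Table 8-5 places Day 14 in Week 2 and Day 15 in Week 3, so Week 12 ends on Day 84.

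A subject who escalates without a hold therefore meets the condition. Section 4.2.1 reports that 40 of 43 subjects in the earlier US study, which started at 50 mg, needed 150 mg. Reaching the top dose is not a remote case, although the documents do not say how many subjects would reach it by Week 12 under this schedule.

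**What do the two instructions give?** For a subject on 150 mg/day in Weeks 13 to 26, with counts taken without transfusion:

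| Platelet count (× 10⁹/L) | Table 6-3 | Sentence, read literally | Difference |
|---|---|---|---|
| below 50 | 150 mg/day (already at the top dose) | 150 mg/day | none |
| 50 to 100 | 150 mg/day | 150 mg/day | none |
| above 100, up to 200 | 125 mg/day at the first step | 150 mg/day | 25 mg/day |
| above 200 | 0, until the count is below 50 | 150 mg/day | 150 mg/day |

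Over the 14 days to the next step:

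- Above 100 and up to 200: 125 × 14 = 1,750 mg against 150 × 14 = 2,100 mg. The table gives 350 mg less, and 350 / 2,100 = 17%.
- Above 200: 0 mg against 2,100 mg for each 14 days of interruption.

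**Does any text set the order?**

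- Section 6.5.1 says that dose follows platelet count and points to the tables. This favours the table but is not a precedence clause.
- Section 4.2.1 gives the aim that "subjects are exposed to the lowest dose necessary to achieve the desired platelet count target" and adds: "These dosing recommendations limit exposure by utilizing the lowest effective dose". This is rationale, not a rule.
- Section 6.5.1 lets the investigator reduce or stop for an adverse event. Section 10.1.1 lets a laboratory value count as one if it is symptomatic, clinically significant or needs therapy.
- Section 6.5.1.2, under a liver heading, allows interruption when clinically indicated. Section 9.1.1 requires stopping if the investigator believes that continuing would harm the subject.
- The SAP contains no dosing rule.

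The last three points on dosing discretion leave room for judgement. None of them is a platelet-count rule.

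**The case against.** The strongest answer is that the sentence sets a ceiling, and on that reading there is no conflict. The wording helps: row 2 of the table tells the site to keep the dose, whereas the sentence speaks of keeping the maximum dose at 150 mg. Section 6.2.4 uses the word in the same way when it defines overdose as a dose "higher than the maximum daily dose (150 mg) of eltrombopag specified in the study protocol". The table's title runs to Week 26, the following sentence assumes that doses can still be decreased, and Section 6.5.1 names the tables as the criteria. All of this stands, and the ceiling is the better reading.

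It does not dispose of the point. Row 1 already states the 150 mg limit, so a reader may look for something more in a separate sentence with its own weeks, and no text tells that reader that the table prevails. It would go too far to say that the Week 12 condition is idle under the ceiling reading. Fastest escalation ends close to that week, and the sentence may simply describe a subject who needed every step and stays at the top dose until the Week 26 assessment.

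Other stronger readings are also open to a reader and are not supported:

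- **That the sponsor intended to hold 150 mg/day whatever the count.** The lowest-dose statements in Section 4.2.1 point the other way.
- **That sites did or will dose differently.** Nothing in the documents shows it, and the discretion described above remains available.
- **That the Week 26 response rate is biased.** The documents give nothing that links the two readings to different response rates.
- **That visit frequency would differ by a fixed number of days.** Any such count depends on which week numbering is used and on how long the dose stays unchanged after a reduction.

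**Conclusion.** The point holds as a minor dosing-safety correction. On a literal reading, the sentence contradicts two mandatory rows of Table 6-3 in the same weeks, by 25 mg/day at the first reduction step and by the full 150 mg/day above 200 × 10⁹/L. On the more probable ceiling reading there is no contradiction, but the protocol does not say so expressly.

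The conflict is confined to subjects at 150 mg/day at Week 12 whose count without transfusion later exceeds 100 × 10⁹/L by Week 26. The documents give no frequency for such counts at that dose, so the number affected is unknown and may be small. No effect on the primary estimate is claimed.

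One limit on the check: Section 6.5.1 mentions a schematic alongside the tables. Figures are missing from the text available here, so a schematic that settles the matter cannot be ruled out.

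**What to change.** Let Table 6-3 govern and reword the sentence as a ceiling:

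*If the dose has reached 150 mg/day by Week 12, it will not be increased further from Week 13 to Week 26; the reduction and interruption criteria in Table 6-3 continue to apply.*

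The cost is one sentence in a protocol amendment or a clarification letter to sites. Design, sample size and analysis are unchanged.

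The SAP's document history lists versions made before the primary, updated and final database locks, so Weeks 13 to 26 may already be past for enrolled subjects. In that case the rewording mainly corrects the record. The dosing listings already planned in SAP Section 2.4.1, read with the platelet counts, would show whether any subject was held at 150 mg/day above 100 × 10⁹/L.

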**Table 6-4 Criteria for dose adjustment of eltrombopag after Week 26**

Standards of hematological value	Dose adjustment
The following values are kept for 8 or more weeks: ▪ Platelet count of $> 50 \times 10^9/L$ , and ▪ Hemoglobin value of $> 100 \text{ g/L}$ under no blood transfusion, and ▪ Neutrophil count of $> 1.0 \times 10^9/L$	Reduce the dose to the 50% dose (see Table 6-5 )
When the above value is kept at the 50% dose for further 8 weeks	Interrupt administration.
When the values decrease to the following ones at the 50% dose : ▪ Platelet count of $< 30 \times 10^9/L$ , or ▪ Hemoglobin value of $< 90 \text{ g/L}$ , or ▪ Neutrophil count of $< 0.5 \times 10^9/L$	The dose can be reinitiated at the previous effective level
When lower than the above values after administration was interrupted tentatively	Administration can be restarted at a dose of 25 mg/day

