**Table 6-5 Dose reduce criteria of eltrombopag after Week 26**

Dose before decrease	50% decreased dose
150 mg/day	75 mg/day
125 mg/day	75 mg/day or 50 mg/day*
100 mg/day	50 mg/day
75 mg/day	50 mg/day or 25 mg/day*
50 mg/day	25 mg/day
25 mg/day	25 mg Qod

\*When eltrombopag dose need to be reduced by 50% from 125 mg/day or 75 mg/day, the investigators will need to select an appropriate dose level (choose either 75 mg or 50 mg daily for subjects treated with eltrombopag 125 mg/day, and 50 mg or 25 mg daily for subjects treated with eltrombopag 75 mg/day) according to subjects' clinical status.

If subject fails to respond after 26 weeks of treatment, he/she will go off study per [Section 3](#) and [Section 9.1.1](#).

For subjects who do not tolerate the protocol-specified dosing schedule, dose interruptions and/or reductions are either recommended or mandated in order to allow subjects to continue the study treatment.

These dose modifications are summarized in [Section 6.5.1.1](#) and [Section 6.5.1.2](#). Permanent treatment discontinuation is mandatory for specific events indicated as such in [Section 9.1.1](#) and [Section 6.2.2](#).

These dose changes must be recorded on the Dosage Administration Record (DAR) – electronic case report form (eCRF).

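### After Week 26 no written rule interrupts eltrombopag for high platelets: the limit of 200 x 10^9/L in Table 6-3 ends and Table 6-4 does not replace it

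*Protocol*

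**What the plan says.** Protocol Section 6.5.1 splits blood-count dosing at Week 26.

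- **Up to Week 26.** Table 6-3 is titled "Criteria for dose adjustment of eltrombopag between Week 1 and Week 26". It has two high-platelet rows, both for counts without transfusion. Above 100 x 10^9/L: "Reduce the dose by 25 mg each every 2 weeks until the platelet count can be maintained at" 100 or lower. Above 200: "Interrupt the drug until the platelet count becomes" less than 50, then restart 25 mg lower (at 25 mg/day if that was the dose at interruption).
- **Hand-over.** The text below that table reads: "The criteria for dose adjustment of this drug after Week 26 are shown in" Table 6-4.
- **After Week 26.** Table 6-4 has four rows:
  1. Halve the dose when platelets above 50, hemoglobin above 100 g/L untransfused and neutrophils above 1.0 have all held for 8 weeks or more.
  2. Interrupt: "When the above value is kept at the 50% dose for further 8 weeks".
  3. Return to the previous effective level if any count falls (platelets below 30, hemoglobin below 90 g/L, neutrophils below 0.5) at the 50% dose.
  4. After such a fall during interruption: "Administration can be restarted at a dose of 25 mg/day".

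Two other tables also apply after Week 26, but neither sets a blood-count criterion. Table 6-5 looks up the "50% decreased dose", and Table 6-6 covers liver signals. Sections 3 and 4.2.1 restate the taper and the restart and add no high-platelet limit.

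**The concern.** The numeric guard against platelet overshoot stops where long-term dosing begins. Responders may stay on drug until product launch (Section 6.1.5). Section 4.2.2 reports that, in the US study, counts in all lineages went on rising with continued exposure. Section 1.3 puts plasma exposure in Asian patients 50% to 90% above that in non-Asian patients. Section 9.1.1 makes thromboembolism a reason to stop treatment. Section 4.2.1 describes the design as using the lowest dose that reaches the platelet target, and gives no reason for ending the platelet limits at Week 26.

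What is at stake is subject safety and consistent dosing across sites in the long-term phase. Dosing also feeds the Week 52 response and the duration of response. It does not touch the Week 26 primary endpoint.

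**Working it through.** The plan has no figure of its own to reproduce here. The check sets the two tables side by side and then sizes the group concerned.

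**Step 1. One count, before and after Week 26** (no transfusion, full dose)

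| Case | Week 25, Table 6-3 | After Week 26, Table 6-4 |
|---|---|---|
| Platelets 250, hemoglobin 95 g/L | Interrupt until below 50 | No row: hemoglobin is not above 100, so no taper; nothing has fallen to the restart levels |
| Platelets 250, all three lineages above the taper levels | Interrupt until below 50 | Halve after 8 weeks; interrupt after 8 + 8 = 16 weeks of sustained values |

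**Step 2. Other text that might fill the gap**

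- Section 6.5.1 says the dose is "titrated in the order of 50 mg, 75 mg, 100 mg, 125 mg and 150 mg/day according to the platelet count of each subject", and Section 6.1.3 has a similar sentence. Neither is limited by week, but both refer to Section 6.5.1 or its tables for the criteria. They therefore lead back to Table 6-4.
- Section 6.5.1 lets the investigator reduce or stop for an adverse event. Section 9.1.1 requires discontinuation for laboratory abnormalities that, in the investigator's judgment, prevent continuing. Neither gives a platelet threshold.

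**Step 3. Subjects on drug but outside the taper rows**

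Inputs: 20 subjects; response rates of 40% (US study) and 47.6% (Japanese study), Section 1.2; in the US study 17 responders, 14 of whom continued in the extension, and 7 trilineage responses, Section 4.2.2.

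- Responders expected: 20 x 0.40 = 8.0; 20 x 0.476 = 9.52.
- Share without a trilineage response, among the 14 who continued (taking the 7 to be among them): (14 - 7)/14 = 50.0%, exact 90% CI 26.4% to 73.6%.
- The same among all 17 responders: (17 - 7)/17 = 58.8%, exact 90% CI 36.4% to 78.8%.
- Product, low end: 8.0 x 0.500 = 4.0. High end: 9.52 x 10/17 = 5.6.

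This gives about 4.0 to 5.6 of 20 subjects. The confidence intervals show how weakly the shares are known. The documents do not say how many subjects would pass 200 x 10^9/L, so the number affected cannot be estimated beyond being some part of this group, plus any three-lineage responders above 200.

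**Step 4. Restarts after interruption** (secondary)

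- Tapered off in the US study: 5 of 17 responders = 29.4%. Here: 8.0 x 5/17 = 2.35; 9.52 x 5/17 = 2.80.
- Relapse after taper: 0 of 5 (Section 4.2.1). One-sided 95% upper limit: 1 - 0.05^(1/5) = 45.1%.
- Restarts at that limit: 2.35 x 0.451 = 1.06; 2.80 x 0.451 = 1.26. So none to about one subject is expected.

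**The case against.** The strongest reply is that the change of criteria is deliberate and that clinical judgment covers the rest. Section 4.2.1 gives a rationale for the trilineage taper, modelled on the US study, and says that it limits exposure. Higher Asian exposure is already met by starting at 25 mg rather than 50 mg. Subjects also arrive at Week 26 after Table 6-3 has cut doses for platelets above 100. Under Section 10.1.1 a clinically significant laboratory value is itself an adverse event, so the discretion clause reaches a platelet rise that the investigator judges significant. Section 4.2.2 describes gradual movement towards normal, not overshoot. The Investigator's Brochure and the study-design figure are not available here.

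Much of this stands. Investigators may act, and the evidence does not show that overshoot is common. But the taper rationale explains why recovered subjects come off drug; it does not explain why a count that required interruption in Week 25 requires nothing later. Discretion without a threshold also leaves each site to set its own.

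The reply is also right on the limit of 100. Carried over unchanged, it would collide with the taper. With platelets of 120, hemoglobin of 110 g/L and neutrophils of 1.5, one rule would cut 25 mg every 2 weeks while the other halves the dose at 8 weeks. A platelet count above 100 is also part of the complete-response definition in Section 5.

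**Conclusion.** The gap is real but narrow: after Week 26 the protocol has no written platelet level at which drug is interrupted. About 4.0 to 5.6 of 20 subjects could be on drug outside the taper rows. That range assumes that all responders continue, that the response rates of the earlier studies apply, and that the trilineage responses in Section 4.2.2 match the taper criteria. The share above 200 is unknown. This is a worthwhile, low-cost improvement and not a threat to the trial's conclusions.

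A reader might infer more, and the documents do not support it:

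- **That no dose table but 6-4 applies after Week 26.** Tables 6-5 and 6-6 apply too; Table 6-4 is the only one with blood-count criteria.
- **That the dose can never be raised, or that a restarted subject is held at 25 mg/day.** Row 3 of Table 6-4 raises the dose from the 50% level. After a restart the protocol is silent on titration; it does not forbid it. With none to about one restart expected, this is a minor clarification.
- **That 12 of 17 (71%) lacked three-lineage recovery.** That counts responders who were not tapered. With 7 trilineage responses, 10 of 17 is the figure.
- **That 0 of 7 is a relapse rate off drug.** Section 4.2.1 describes those seven as having maintained response, so the group is defined by its outcome. The five who were tapered are the cleaner base.

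**What to change.** Add one row to Table 6-4: platelets above 200 x 10^9/L without transfusion interrupt eltrombopag until below 50, then restart 25 mg lower (25 mg/day if the dose was already 25 mg/day). State that this row takes precedence over the taper rows and the 25 mg/day restart row. Without that statement the two restart rules would conflict, since one acts below 50 and the other below 30, at different doses.

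Two matters are for the sponsor. One is whether to keep the above-100 reduction alongside the trilineage taper. The other is a short note on whether, and on what criteria, the dose may be raised after a 25 mg/day restart.

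The cost is a protocol amendment with IRB/IEC and, where required, health authority approval (Section 14.1). Each dose change also returns the subject to 2-weekly visits until the dose has been unchanged for 4 weeks (Table 8-1), with 2-weekly liver tests during adjustment (Section 6.5.1.2). No new type of assessment is needed: blood smears are scheduled at every treatment visit, including the extension, with hematology on the same day (Table 8-1, Section 8.4.4). No analysis changes. The SAP provided is the one for the final analysis, so the change may come late for this study.
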